### **8.3. Subject Withdrawal Criteria**

An early termination occurs when a subject who provides written informed consent ceases participation in the study, regardless of circumstances, before the completion of the study. Subjects may voluntarily withdraw from the study at any time for any reason. In addition, the Investigator or the Medical Monitor may terminate a subject's study participation for reasons related to the best interest of the subject. Subjects who terminate from the study will not be replaced. Subjects may be terminated from the study due to any of the following reasons:

- Non-compliance
- Lack of efficacy
- Lost to follow-up
- Protocol violation
- Withdrawal by subject
- AE
- Death
- Other

If a subject is discontinued from the study before completing Month 12, then to the extent possible, all assessments, including safety, that are scheduled to be performed at Month 12 should be performed on the day of discontinuation.

[figure not shown]
Subjects who discontinue prematurely will not be replaced.

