Sirolimus for ocular administration is being tested with a proprietary formulation, DE-109 for the treatment of non-infectious, posterior uveitis. This proprietary formulation was originally developed by MacuSight, Inc. and in June 2010, Santen, Inc. acquired the worldwide rights to the formulation. The formulation provides drug exposure to the retina/choroid for up to approximately 2 months, and is amenable to delivery by the intravitreal route of administration. The active pharmaceutical ingredient in the formulation is sirolimus. Sirolimus, also known as rapamycin, was isolated in the 1970's from *Streptomyces hygroscopicus* in soil samples from Easter Island (Napoli et al., 2001). Sirolimus is the active pharmaceutical ingredient in 2 products approved by the FDA, specifically Rapamune®, an immunosuppressive agent used in renal transplant patients, and the CYPHER® sirolimus-eluting Coronary Stent approved for improving coronary luminal diameter in patients with symptomatic ischemic disease.

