### **9.2.2.      Rescue Therapy**

Rescue therapy may be used at the discretion of the Investigator.

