### **9.3.      Treatment Compliance**

The Investigator is not required to administer DE-109 at any visit. DE-109 treatments may be given, as needed, at the discretion of the Investigator; however, DE-109 treatments may not be given more frequently than every 60 days.

The Investigator is responsible for scheduling the subject for follow-up visits based on the Investigator's standard clinical procedures and these visits are not study visits. If a subject receives treatment with DE-109 (440  $\mu$ g) between scheduled study assessments, the visit will be a Post-Baseline PRN Treatment Visit and procedures will be performed and recorded as specified in this protocol (See [Table 3](#)).

Study monitors will verify pertinent data to confirm the study is conducted according to the protocol.

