## 12. ASSESSMENT OF SAFETY

### 12.1. Adverse Events, Serious Adverse Events and Events of Special Interest

#### 12.1.1. Definition of Adverse Events

An AE is any untoward medical occurrence in a subject administered a pharmaceutical product and which does not necessarily have a causal relationship with study drug. An AE therefore can be an unintended sign (including an abnormal laboratory finding), symptom, or disease temporally associated with the use of a medicinal (investigational) product, whether or not related to the medicinal (investigational) product.

In clinical studies, an undesirable medical condition occurring at any time, including baseline or wash-out period, may be recorded as an AE even if no study drug has been administered.

Any significant change in a subject's condition from baseline, regardless of causality, is to be considered an AE, unless the change is determined to be a continuation of a pre-existing condition that is documented in the subject's medical history. However, a clinically significant worsening in severity, intensity, or frequency of a pre-existing condition may indicate an AE.

Lack of efficacy of the study drug for the condition being investigated is not considered an AE unless a clinically significant change is assessed by the Investigator. In addition, any elective surgical procedure scheduled or planned prior to study entry is not considered an AE and the underlying diagnosis for which surgery is to be performed should be captured in the medical history as a pre-existing condition.

For this protocol, an AE is any *on-study* untoward medical occurrence (e.g. sign, symptom, disease, syndrome, intercurrent illness) that occurs in a study subject, regardless of the suspected cause and regardless of timing of DE-109 (440 µg) administration. An on-study AE can occur anytime after the date of informed consent through the last study visit. An AE will be considered as *treatment-emergent* if the AE occurred on or after the date of the first DE-109 (440 µg) treatment up to the last study visit. Treatment-emergent AEs are a subset of on-study AEs. Both on-study and treatment-emergent AEs will be reported.

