#### 12.1.1.2. Reporting Adverse Events

AEs, whether spontaneously reported by the subject or noted by authorized study personnel, will be recorded in the subject's medical record and on the appropriate AE eCRF. Each recorded AE will be described by its duration (i.e., start and end dates), severity, regulatory seriousness criteria if applicable, suspected relationship to the study drug, and actions taken.

AEs that occur after any subject has provided written informed consent up to Month 12 must be recorded. If an adverse event is ongoing at the time of study exit, then the Investigator should perform reasonable follow-up efforts as necessary (e.g. telephone contact, post-study office visit) to determine the outcome of the event. To improve the quality and precision of acquired AE data, Investigators should observe the following guidelines:

- Whenever possible, use recognized medical terms when recording. Do not use colloquialisms and/or abbreviations.
- If known, record the diagnosis (i.e., disease or syndrome) rather than component signs and symptoms (e.g., record congestive heart failure rather than dyspnea, rales, and cyanosis). However, other events that are considered unrelated to an encountered syndrome or disease should be recorded as individual AEs (e.g., if congestive heart failure and severe headache are observed at the same time and are clinically unrelated, each event should be recorded as an individual AE).
- AEs occurring secondary to other events (e.g., sequelae) should be identified by the primary cause. A primary AE, if clearly identifiable, generally represents the most accurate clinical term. If a primary AE is recorded, events occurring secondary to the primary event should be described in the narrative description of the case.

For example:

The subject developed orthostatic hypotension and subsequently fainted and fell to the floor wherein she experienced a head trauma and neck pain.

The primary AE in this example is orthostatic hypotension.

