### **12.1.3. Sight Threatening Events**

For the purposes of this study the following ocular adverse events will be reported as serious adverse events:

- Loss of 6 or more lines of vision ( $\geq 30$  letters) from Baseline;
- Endophthalmitis;
- Purulent, infectious conjunctivitis;
- Retinal detachment;
- IOP  $> 35$  mmHg that persists for at least 7 days despite pharmacologic therapy;
- Other significant ocular events per Investigator's discretion

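### SAP 8.3 tabulates BCVA letter gain/loss categories at Month 12 only, so subjects whose last BCVA falls on or before Day 307 are missing from that table; add the same table at Study Exit

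*Protocol*

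**What the plan says.** Protocol 8.3 covers early exit. It reads "Subjects may be terminated from the study due to any of the following reasons" and lists non-compliance, lack of efficacy, loss to follow-up, protocol violation, withdrawal by the subject, AE, death and other. For a subject discontinued before Month 12 it asks, to the extent possible, that "all assessments, including safety, that are scheduled to be performed at Month 12 should be performed on the day of discontinuation". BCVA is one of those assessments (Protocol 7.5.2 and Table 3).

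SAP 8.3 has two BCVA outputs that matter here:

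- BCVA and its change from baseline are summarised and listed at Month 12 and at the Study Exit visit.
- The counts of study eyes that gained or lost at least 5, 10 or 15 letters, or stayed within 5 letters, are specified at Month 12 only.

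SAP 4.1.2 defines the Study Exit visit as the Month 12 or early termination visit. If both are missing it is the last visit before the exit date, and if there is no visit after Day 1 it is Day 1 itself. SAP 4.1.5 and Table 2 assign every post-baseline visit, early termination visits included, to an analysis visit by study day. SAP 6.2.1 uses observed data only.

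**The concern.** Long-term safety is the study's only objective, and the letter-category table is the most readable vision-safety output in the SAP. As specified, it describes only subjects with a BCVA late enough to count as Month 12. A subject who loses 15 letters and leaves at Day 200 contributes to a mean and to a listing, but not to the table a reader would consult for the share of study eyes that lost 15 letters.

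If leaving is linked to visual outcome, the Month 12 shares describe those who stayed and may differ from the shares among all subjects. If it is not linked, nothing is biased and only numbers are lost. The documents do not say which applies.

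The omission also looks unintended, since the SAP reports the comparable VH and ophthalmoscopy outputs at Study Exit.

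**Working it through.** **Inputs.** Analysis windows from SAP Table 2; 60 subjects from SAP 3.3; planned exit at Day 360 with a window of ±14 days from Protocol 7.5.2; no imputation from SAP 6.2.1. The documents give no exit rate and no letter-loss rate, so there is no plan figure to reproduce.

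**Step 1: the cut-off.** The windows reproduce both worked examples in SAP 4.1.5: Day 125 lies in [68, 127] and maps to Month 4, and Day 250 lies in [248, 307] and maps to Month 10. At the boundary, Day 307 maps to Month 10 and Day 308 to Month 12. A subject whose last BCVA is on or before Day 307 has no Month 12 record, and no value is carried forward. Exits up to 307/360 = 85.3% of planned follow-up are therefore omitted. The rule is already lenient at the late end: Month 12 opens at Day 308, which is 346 − 308 = 38 days before the visit window.

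**Step 2: comparison with the other eye outputs in the SAP.**

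| Output | Month 12 | Study Exit |
|---|---|---|
| VH score, change, shift (8.2) | yes | yes |
| BCVA value and change (8.3) | yes | yes |
| BCVA 5/10/15-letter categories (8.3) | yes | **no** |
| IOP change from baseline (8.4) | not named | yes |
| Ophthalmoscopy and cataract shifts (8.5) | not named | yes |

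The letter-category table is the only one of these outputs without a Study Exit version.

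**Step 3: a bound that needs no letter-loss rate.** Let n be the number of the 60 subjects omitted and x the number at Month 12 who lost at least 15 letters. From the Month 12 table alone, the all-subject share lies between x/60 and (x + n)/60, an interval n/60 wide. With n assumed:

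- n = 0: width 0
- n = 1: 1/60 = 1.7 points
- n = 6: 6/60 = 10 points
- n = 15: 15/60 = 25 points

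For example, with n = 6 and x = 3 (both assumed), the table shows 3/54 = 5.6%, which is compatible with 3/60 = 5.0% up to 9/60 = 15.0%. The planned Study Exit listing closes this interval for every early exit with a post-baseline BCVA. The bound therefore measures what the table leaves open, not what the study leaves unknown.

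**Step 4: illustration with assumed rates.** Take 6 early exits, with 5% of the 54 others losing at least 15 letters. The Month 12 table is then expected to show 5.0%. The expected Study Exit share depends on the loss rate among early exits:

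- 10%: (54 × 0.05 + 6 × 0.10)/60 = 3.3/60 = 5.5%
- 30%: (2.7 + 1.8)/60 = 7.5%
- 50%: (2.7 + 3.0)/60 = 9.5%

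If both groups lose vision at the same rate, the two tables agree.

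**The case against.** **The data are already reported.** The Study Exit BCVA change is summarised, with minimum and maximum (SAP 6), and listed. With 60 subjects, a reader can count the 15-letter losses by hand. This stands, and it limits the point to a missing table. A mean can still hide a few large losses, and leaving the count to the reader is a weak substitute for a specified table.

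**Vision loss has other routes into the tables.** Protocol 12.1.1 treats any significant change from baseline as an AE. The sight-threatening list includes "Loss of 6 or more lines of vision" and also other significant ocular events at the investigator's discretion. Protocol 14.6 lists clinically significant changes. All true, so a reader should not infer that losses in early exits go unreported. Below 30 letters, however, these routes depend on investigator judgement and give no count by letter category.

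**A fixed time point is defensible.** A Study Exit table mixes short and long follow-up. This stands too, and is why the new table should supplement the Month 12 table.

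**A stronger reading.** A reader might infer that Protocol 8.3 forces subjects who stop DE-109 out of the study and so biases the safety results. The text does not support that. The wording is permissive, and with death, loss to follow-up and other on the list it also reads as a set of disposition categories. Protocol 9.3 says "The Investigator is not required to administer DE-109 at any visit", Protocol 9.2.2 says "Rescue therapy may be used at the discretion of the Investigator", and the Safety population keeps subjects who are never injected (Protocol 14.2). An investigator can already withhold drug and keep the subject to Month 12.

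Follow-up after exit is thinner: an on-study AE runs only to the last study visit (Protocol 12.1.1), while Protocol 12.1.1.2 says "AEs that occur after any subject has provided written informed consent up to Month 12 must be recorded", which is unclear for someone who has left. But AEs reported at exit are followed (12.1.5). Taking drug exposure as about 60 days (Protocol 5), even an assumed 15 exits would leave at most 15 × 60 = 900 of 60 × 360 = 21,600 planned subject-days, or 4.2%, as exposed time unobserved. The withdrawal text of US Amendment 01, under which 13 of the 60 subjects consented, is not among the documents and could not be checked.

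**Conclusion.** The gap is real and narrow. The letter-category table omits every subject whose last BCVA is on or before Day 307, whatever the reason for leaving, including death, loss to follow-up and voluntary withdrawal. It is a gap in SAP 8.3, not an error in Protocol 8.3, and no change to the withdrawal criteria would close it fully.

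The size is unknown. It is zero if nobody leaves early, and n/60 of the all-subject share if n leave and only the Month 12 table is read. The direction of any difference is also unknown. The study is descriptive with no hypothesis test, so no error rate or power is affected. The change is still worth making: safety is the sole objective, the data are already collected, and the SAP already uses Study Exit for the other eye measures.

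**What to change.** In SAP 8.3, also tabulate study-eye gain and loss of at least 5, 10 and 15 letters, and maintenance within 5 letters, at the Study Exit visit. Keep the Month 12 table as it is. Add two details:

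- Count subjects with no post-baseline BCVA in a separate row. SAP 4.1.2 makes Day 1 the exit visit when nothing follows it. SAP 4.2.3 defines change only at a post-baseline visit, so a change of 0 is probably not intended; the row makes sure such a subject is not counted as maintained.
- Show the study day of the exit BCVA, because follow-up times differ and the exit visit may be the last visit before the exit date.

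The cost is one table and one row rule in the SAP, with no new data. The downside is the mixture of follow-up times, which the study-day display makes visible.

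Optional and secondary: Protocol 8.3 could state that stopping DE-109 for an AE or lack of efficacy does not by itself require leaving the study. This would clarify permissive text. It needs an amendment with ethics re-approval and would help only subjects still on study. With enrolment complete by 18 November 2016, the last Day 360 falls no later than 12 November 2017 (18 November 2016 plus 359 days). Subjects who stay would also remain barred from other investigational trials (Protocol 9.2.1).

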## 9. TREATMENT OF SUBJECTS

### 9.1. Description of Study Drug

DE-109 is a depot formulation of sirolimus, an immunomodulatory agent which inhibits the mammalian target of rapamycin (mTOR), a serine/threonine protein kinase that regulates cell growth, proliferation, motility and survival through changes in transcription and protein synthesis.

**Figure 1: DE-109 Chemical Structure**

Investigational Product: 2.0% DE-109 injectable solution (440 µg)

### 9.2. Concomitant Medications

The use of any concomitant prescription or over-the-counter medication will be recorded during the study. Therapy considered necessary for the subject's welfare may be given at the discretion of the Investigator during the study. Whenever possible, concomitant medications should be administered in dosages that remain constant throughout the study. The generic name, indication, route of administration, frequency, dose, start date and stop date (if applicable) will be recorded for each medication.

#### 9.2.1. Prohibited Medications or Treatments

The decision to administer a prohibited concomitant medication or treatment during the study should be made with the safety of the subject as the primary consideration. There may be prohibited therapies not mentioned below.

The following medications or treatments are prohibited:

- Participation in other investigational drug (SAKURA is an exception) or device clinical trials within 30 days prior to Day 1 or planning to participate in other investigational drug or device clinical trials for the duration of the study. This includes both ocular and non-ocular clinical trials.
- Therapeutic radiation to the head or neck within 90 days prior to Day 1 and throughout the study.
- Use of medically prescribed marijuana or other illegal medication within 30 days prior to Day 1 and throughout the study.

### **9.2.2.      Rescue Therapy**

Rescue therapy may be used at the discretion of the Investigator.

### **9.3.      Treatment Compliance**

The Investigator is not required to administer DE-109 at any visit. DE-109 treatments may be given, as needed, at the discretion of the Investigator; however, DE-109 treatments may not be given more frequently than every 60 days.

The Investigator is responsible for scheduling the subject for follow-up visits based on the Investigator's standard clinical procedures and these visits are not study visits. If a subject receives treatment with DE-109 (440  $\mu$ g) between scheduled study assessments, the visit will be a Post-Baseline PRN Treatment Visit and procedures will be performed and recorded as specified in this protocol (See [Table 3](#)).

Study monitors will verify pertinent data to confirm the study is conducted according to the protocol.

### **9.4.      Randomization and Masking**

Randomization is not employed in this study. The decision to administer study drug on any given study day is at the discretion of the Investigator. All subjects who are dosed will receive the same open-label dose of DE-109 (440  $\mu$ g). Study drug will contain a unique number and should be dispensed in sequential, ascending order by each center.

## 10. STUDY DRUG MATERIALS AND MANAGEMENT

### 10.1. Study Drug

#### 10.1.1. Test Article

DE-109 (440 µg) is formulated as clear, non-aqueous solutions of the drug substance, sirolimus, in a vehicle composed of polyethylene glycol 400 (PEG 400) and ethanol. Both PEG 400 and ethanol are widely used as solubilizing excipients in injectable formulations (Strickley, 2004).

The dosage of sirolimus to be administered in this extension study will be 440 µg DE-109 as shown in [Table 4](#).

**Table 4: DE-109 Dosing**

Injection Volume of:	Will deliver approximately:
20 µL of 22 µg/µL (2.0%) intravitreally	440 µg of sirolimus

DE-109 (440 µg) will be supplied frozen either as 0.3 mL of sterile injectable solution in 0.5 mL vials or 0.3 mL of sterile injectable solution in 2 mL vials. Investigator must use the syringes and needles supplied by the sponsor.

#### 10.1.2. Study Drug Complaint Reporting

Complaints regarding the study drug should be reported to Santen Product Complaint at [contact] or the study monitor.

### 10.2. Study Drug Packaging and Labeling

DE-109 (440 µg) injectable solutions are filled in Type 1 Glass (borosilicate) clear vials, capped with 13 mm Gray Butyl stoppers with B2-40 coating, and sealed with a 13 mm colored Flip-Off Truedge. Each single use vial will be placed in a unit carton, and the labeling will include protocol number, unique kit number, and storage conditions.

### 10.3. Study Drug Storage

DE-109 (440 µg) will be received frozen. DE-109 (440 µg) must be stored and should remain frozen in a secure, locked, dark, temperature controlled,  $-20^{\circ}\text{C} \pm 5^{\circ}\text{C}$  (with allowable temperature excursions up to  $-35^{\circ}\text{ C}$ ) freezer with restricted access until the time of use.

### 10.4. DE-109 Preparation

The vial of study drug will be removed from the freezer and thawed by rotating the vial between the palms of the hands for a minimum of 5 minutes, or by setting the vial at room temperature for a minimum of 30 minutes. Care should be taken to protect the product from light. Study drug should be drawn into the provided single-use plastic syringe within 60 minutes after removing

the vial from the freezer. Study drug should be injected within 2 hours of being drawn up into the single-use syringe.

Each vial contains enough study drug to inject one subject. Each vial will be used one time only.

A sterile, single-use 250  $\mu$ L syringe custom marked at 20  $\mu$ L will be provided separately for intravitreal injection use. These will be used for intravitreal injections of DE-109. Instructions for filling the syringe are as follows:

1. Remove the sterile, single-use 250  $\mu$ L syringe custom marked at 20  $\mu$ L from the packaging.
  - a. If the drug product is dispensed from a 0.5 mL vial, attach a 23-gauge x 1 inch or 25-gauge x 5/8 inch needle to the syringe.

**Figure 2: 0.3 mL fill in a 0.5 mL vial**

- b. If the drug product is dispensed from a 2 mL vial, attach a 21-gauge x 1 1/2 inch needle to the syringe.

**Figure 3: 0.3 mL fill in a 2 mL vial**

2. Using sterile technique, carefully draw up **more than 20  $\mu$ L** of DE-109 into the plastic syringe. It should be noted that due to the slight viscosity drawing up DE-109 will be slow.
  3. For DE-109 (440  $\mu$ g) preparation, replace the needle with a 30-gauge x 0.5 inch needle for the intravitreal injection.
    - a. Ensure that the 30-gauge x 0.5 inch needle is affixed tightly to the syringe.
    - b. **ALIGN THE TOP EDGE OF THE RED O RING OF THE PLUNGER WITH THE 20  $\mu$ L BLACK MARK ON THE SYRINGE** (See [Figure 4](#)).
    - c. PLEASE ENSURE THAT THERE ARE NO AIR BUBBLES WITHIN THE SYRINGE OR THE NEEDLE HUB PRIOR TO INJECTION.

**Figure 4: The alignment of the syringe**

## **10.5. Administration**

### **10.5.1. Instructions for Intravitreal Injection of DE-109**

#### **10.5.1.1. Eye Preparation**

The subject may receive DE-109 (440 µg) treatments at the discretion of the Investigator, but no more frequently than every 60 days. Instructions for ocular antisepsis are provided below.

1. Dilate pupil (1% Mydriacyl and 2.5% phenylephrine or equivalent applied topically) approximately 10 minutes prior to injection;
2. Administer 1 eye drop of topical anesthetic (0.5% proparacaine hydrochloride ophthalmic solution or an equivalent topical ophthalmic anesthetic);
3. Administer 5% povidone iodine to the study eye immediately prior to injection.
4. Use a sterile cotton-tipped applicator to remove excess fluid from the lower conjunctival sac;
5. Take 2 sterile cotton tipped applicators and thoroughly soak with 0.5% proparacaine topical anesthetic eye drops or an equivalent topical ophthalmic anesthetic. Place the soaked applicators, side by side, gently but firmly on the superotemporal conjunctival surface at the area of the entry site described below in Step 10 and hold in place for approximately 1 minute;
6. Administer a subconjunctival injection of 0.25 mL of 2% lidocaine without epinephrine or equivalent to the superotemporal quadrant to the area of the entry site described below in Step 10 (Steps #5 and 6 may be omitted per the Investigator's discretion);

7. Insert sterile eyelid speculum;
8. Place sterile eye drape over study eye;
9. Prior to starting the injection procedure, DE-109 should have been prepared as described in Section 10.4, with the appropriate dose of study drug drawn into a 250  $\mu$ L single-use plastic syringe. **ENSURE THAT THERE ARE NO AIR BUBBLES IN THE SYRINGE OR NEEDLE HUB;**
10. If the subject is phakic, the entry site is recommended to be 3.5 mm to 4.0 mm peripheral to the inferotemporal limbus. If the subject is aphakic or pseudophakic, the entry site is recommended to be 3.0 mm to 3.5 mm peripheral to the inferotemporal limbus. A caliper may be used to identify the needle entry site. The intravitreal injection site may be modified at the Investigator's discretion.
11. Insert the needle perpendicular to the eye wall at the location specified in Step 10.
12. Very slowly, inject the entire study drug volume and hold for 5 seconds prior to slowly withdrawing the needle. Do not pull back on the plunger at any time prior to withdrawing the needle;
13. Briefly apply pressure for approximately 1 minute to the needle entry site with a sterile cotton tipped applicator;
14. Remove the eyelid speculum;
15. Patch the study eye at the Investigator's discretion;

Prescribe fluoroquinolone equivalent antibiotic eye drops 3 times per day for 2 days following each injection ([Aiello et al., 2004](#)).

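### The optional anaesthetic steps name the superotemporal area as the Step 10 entry site, but Step 10 recommends the inferotemporal limbus

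*Protocol*

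**What the plan says.** Protocol 10.5.1.1 gives the injection procedure as one numbered list.

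- **Step 2** gives every eye a topical drop: "Administer 1 eye drop of topical anesthetic".
- **Step 5** places two anaesthetic-soaked applicators "gently but firmly on the superotemporal conjunctival surface at the area of the entry site described below in Step 10".
- **Step 6** gives 0.25 mL of 2% lidocaine subconjunctivally "to the superotemporal quadrant to the area of the entry site described below in Step 10". It adds that "Steps #5 and 6 may be omitted per the Investigator's discretion".
- **Step 10** states, for phakic eyes, that "the entry site is recommended to be 3.5 mm to 4.0 mm peripheral to the inferotemporal limbus" and, for aphakic or pseudophakic eyes, that "the entry site is recommended to be 3.0 mm to 3.5 mm peripheral to the inferotemporal limbus". Its other two sentences allow a caliper and let the Investigator modify the site.
- **Step 11** fixes the needle position: "Insert the needle perpendicular to the eye wall at the location specified in Step 10".
- **Step 13** begins "Briefly apply pressure for approximately 1 minute to the needle entry site" and names no quadrant.

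**The concern.** Steps 5 and 6 each describe their target in two ways, by quadrant and by reference to Step 10, and treat the two as the same place. Under the Step 10 recommendation they are different places.

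This is a working instruction for an invasive procedure that a subject may undergo repeatedly, at intervals of at least 60 days. A site that injects at the recommended location but takes the quadrant word literally would anaesthetise tissue the needle does not enter. If it also performs Step 6, the subject receives a subconjunctival puncture there without the intended benefit. Comfort and procedural safety are at stake; the statistical results are not.

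**Working it through.** There is no stated figure to reproduce, and the conflict itself needs no arithmetic. The check sets the steps side by side.

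| Step | Action | Quadrant named | Tied to Step 10? |
|---|---|---|---|
| 5 | Soaked applicators | Superotemporal | Yes |
| 6 | Subconjunctival lidocaine | Superotemporal | Yes |
| 10, first sentence | Entry site, phakic | Inferotemporal | – |
| 10, second sentence | Entry site, aphakic or pseudophakic | Inferotemporal | – |
| 11 | Needle insertion | None | Yes |
| 13 | Pressure on entry site | None | No |

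1. **Recommended site used, Step 5 or 6 performed.** The needle enters inferotemporally (Steps 10 and 11). The anaesthetic cannot be both superotemporal and at that site. This holds for either lens status.
2. **Recommended site used, cross-reference followed.** The anaesthetic is given inferotemporally, matching the needle, and the quadrant word is ignored.
3. **Site moved to the superotemporal quadrant under Step 10 discretion.** All the wording agrees, but only because the recommendation has been set aside.
4. **Steps 5 and 6 omitted.** No conflict arises.

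The first case is the defective one. The text does not say whether the quadrant word or the cross-reference governs.

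**Could something else settle it?** Step 13 does not. The protocol's list of figures covers the chemical structure, two vial fills and the syringe alignment, so no missing figure shows an injection site. No other part of the supplied protocol or SAP names the intended quadrant.

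**When would a notice to sites cease to matter?** SAP 3.3 says enrolment was completed by 18 November 2016. Assume the last subject's Day 1 was no later than that date. The SAP counts Day 1 as the reference day (4.1.3) and sets the Month 12 visit window at Days 346 to 374 (Table 2).

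- Day 360 = 18 November 2016 + 359 days = 12 November 2017.
- Day 374 = 18 November 2016 + 373 days = 26 November 2017.

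The Protocol's Table 3 schedules no DE-109 administration at Month 12, so on this assumption dosing would have ended before that visit.

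**The case against.** The strongest reply is that the practical effect is close to nil. Steps 5 and 6 may be skipped, the Step 10 site is only a recommendation, and both anaesthetic steps point explicitly to the entry site. A competent injector will have chosen the site before numbing the eye and will numb that place. Nothing in the documents suggests that any site did otherwise. This is fair, and it keeps the point minor. It does not remove the conflict: a site that performs these steps at the recommended location still receives two incompatible directions.

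A second objection is that the documents do not show which quadrant word is the drafting error. If the error is in Step 10, deleting the word from Steps 5 and 6 leaves it as the only quadrant named. That is true, and it is a reason for the clinical team to confirm the intended quadrant. Even so, after the deletion the anaesthetic follows the needle wherever the Investigator injects, so the deletion is sound whichever word was wrong.

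A third objection concerns versions. The SAP applies to US Amendment 01, which schedules visits at Months 2 to 10. The supplied protocol schedules only Day 1 and Month 12, so the amendment's injection section is not visible. This stands as a limit: the finding is about the supplied text and says nothing about the wording under which the 13 of 60 subjects who signed that amendment were later dosed.

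**Conclusion.** The inconsistency is real and minor. Both anaesthetic steps that name a quadrant say superotemporal, and both Step 10 sentences that name one say inferotemporal. It bites only when the recommended site is used, Step 5 or 6 is performed, and the quadrant word is taken literally.

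The number of affected injections is unknown. The documents do not report the quadrant used, how often Steps 5 and 6 were omitted, or how many injections were given under this text, so no ceiling is offered. The study is descriptive, with no hypothesis test, and no planned summary changes.

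**What to change.** In Step 5, delete the single word superotemporal. In Step 6, delete the four-word phrase that names the quadrant. Both sentences still read correctly, and both then depend on the Step 10 reference, including any site the Investigator has modified. Alternatively, have the clinical team decide on one quadrant and state it in Steps 5, 6 and 10.

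Carry the correction into any amendment or later protocol that reuses this procedure. Tell sites only if subjects are still being dosed; on the enrolment assumption above, a notice is moot after 26 November 2017 at the latest.

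The cost is five deleted words in two optional steps, with no change to data collection or analysis.
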